Aim 1: To identify Veteran and surgeon factors associated with preference for endovascular or open repair. We will use validated survey instruments to determine repair type preference (endovascular or open) for Veterans and surgeons, and identify domains in our survey associated with each repair type.

Hypothesis (H1): We hypothesize Veterans who prioritize concerns about pain or disability will prefer endovascular repair, and Veterans who prioritize concerns about durability will prefer open repair.

Aim 2: To determine the effect of the decision aid on agreement between preference and repair type. AAA growth rate estimates suggest 85% of our cohort will undergo repair within our two – year study period. Among patients in the intervention and control groups who undergo repair, we will compare how commonly Veterans receive the repair type they indicated as their preference. We will study potential explanatory variables from our survey, such as AAA knowledge, between the intervention and control groups. Patient satisfaction and shared decision making will be assessed in both the intervention

and control groups.

Hypothesis (H2): Our intervention will be associated with better agreement between preference and treatment type for Veterans with AAA, as well as higher post-operative satisfaction and greater shared decision-making.

2. Study Team

[name], the Principal Investigator, is a VA vascular surgeon and Co-Director of the VA Outcomes Group in White River Junction. A current NIH K08 awardee in health services research, he is experienced in conducting multicenter, cluster-randomized clinical trials^{61, 62}. He is currently the Principal Investigator of a multicenter cluster-randomized trial of a smoking cessation quality improvement intervention funded by the Society for Vascular Surgery⁶². [name] has assembled a team (Table 1) with extensive expertise in survey research ([name]), shared decision-making ([name]), and analyzing outcomes in VA (Drs. [name] and [name]). Finally, [name] and his team members have worked together before in several projects^{63, 64}, many of which have studied physician practice⁶⁴⁻⁶⁶, so they are well prepared to collaborate effectively in this study. Their team, including 20 site PIs, have collaborated on several projects which have studied physician practice⁷¹⁻⁷³ and each has significant time dedicated towards the proposal.

Table 1: Key Personnel

Team Member	Role	Skill Set	Task Aims

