- iv. Inviting Veterans who are candidates to participate in the study: Once a candidate has been identified, the Study Coordinator will note the time of the Veteran's appointment. When the Veteran arrives for their appointment, they will check in as usual and proceed to the waiting room. The first contact with potential participants will be made by The Study Coordinator or other Study Team member who will take the Veteran to a consult room. Once in the consult room, the Study Coordinator or other Study Team Member will use the Study Introduction Script (Appendix 5), to describe the intervention to the Veteran (decision aid and survey) and invite them to participate. Veterans will be offered some time to review the consent form. If they wish to have more time to discuss it with their family and friends, they may reschedule their appointment and return on a later day. The Veteran will be informed that they will be remunerated \$50 at the completion of their first appointment for their time spent completing study documents and surveys.
- v. Consent process: Once a Veteran has expressed interest in the study, the Study Coordinator or other Study Team Member will review the consent form with them, answer any questions, and obtain consent. For any Veterans who are unable to read, the study coordinator will read the consent form to them in the presence of a witness. A witness is required to be present during the entire consenting process for illiterate participants and the witness will sign the informed consent to indicate he/she witnessed the participant "making their mark" consenting to be in the study. After consent has been obtained by the study coordinator, the Veteran will be taken through the survey process.

Step D: Survey administration at intervention and control sites:

Process at the Intervention Sites:

Step 1: The Pre-Survey will be administered with the Veteran by the Study Coordinator. (2 minutes)

Step 1a: The Study Coordinator will review the Decision Aid with the Veteran. (5-10 minutes)

Step 1b: The Study Coordinator will administer the Survey. (10 minutes)

Step 2: The Study Coordinator will escort the patient to the visit with the vascular surgeon.

Step 3: After the Visit, the Study Coordinator will complete the Decision-Process Score with the Veteran. (5 minutes)

Step 4: Thirty days after AAA repair, the Study Coordinator will complete the PSQ-18 with the Veteran. (5 minutes).

The decision aid is available in English and Spanish.

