Aim 1. Dependent and Independent Variables: The main dependent variable in Aim 1 is the preference for repair type (endovascular or open) as expressed by Veterans and surgeons in their respective survey instruments. Each survey instrument has a validated coding algorithm which will be used to categorize survey responses into preference for endovascular or open repair (Appendix 2)⁴⁴. Independent variables, such as age, gender, race, ethnicity, and other descriptive variables are recorded as part of the survey instrument by the Site Study Coordinator. Hospital and surgeon characteristics such as annual hospital and surgeon volume of endovascular and open repair for each participating site will be collected via VINCI by [name]. These variables will be measured at the hospital level, as in prior analyses.^{65, 97-100}

Aim 1: Data analytic strategy: tests, strengths, limitations, and alternative approaches: In Aim 1, our main outcome variable will be Veteran and surgeon preference for repair type (endovascular or open repair). The preference will be defined as either preference for endovascular or preference for open repair. Repair type preference will be categorized from several questions in our survey instruments. Several questions allow for differing degrees of choice (e.g., strongly/slightly favor open repair). For these responses, we will use variables that allow this category. We will use a coding algorithm (Appendix 2) which deconstructs survey questions into components that generate binary outcomes (i.e., preference for open or endovascular repair) and allows sensitivity analyses using the gradients. We will compare the proportion choosing each repair type in the intervention and control groups to test the effect of the decision aid on repair type preference. The proportions preferring each repair type will be compared between the two groups accounting for clustering of patients within center and/or surgeon; in particular, we will use the Mantel-Haenszel test (for stratified contingency tables, equivalent to partial likelihood ratio test from fixed effects logistic regression) or a mixed effects logistic regression with fixed effect of group, and random intercept for center effects.

Aim 1 Data Collection Strategy: potential problems and solutions Refer to Section 6 of this Protocol Coding Guide and Data Management Plan.

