To identify patient characteristics (such as survey responses) associated with preference for endovascular or open repair we will use multivariable mixed effects logistic regression. The use of mixed effects is to account for clustering within individual VA centers using a random intercept, e.g. $\text{logit } \text{Pr}[Y_{ij}=1]=X_{ij}\beta+\mu_i$ where Y_{ij} is the binary preference variable in subject j from cluster i , X_{ij} is a vector of characteristics, μ_i is a random intercept from a zero mean distribution with standard deviation to be estimated (e.g. normal), and β is a vector of coefficient(s). We will explore the feasibility (e.g. convergence) and sensitivity of findings of patient characteristics of using either a random intercept for surgeon, or for center, or for surgeon nested within center. We will report both unadjusted and adjusted estimates, after identifying one or more models to adjust for using for instance stepwise regression or LASSO. Stata (e.g., xtmelogit) and/or R (library lme4 or nlme) software will be used. [name] has extensive experience in these strategies.

Missing Data: To accommodate missing data where justified (e.g. the variable with missing data is predictive and deserves to be adjusted for, and furthermore the data is believed to be missing at random) we shall use multiple imputation methods, such as implemented in the Stata *mi* routine.

Power Analysis: Comparing the effect of the decision aid on repair type preference. Because the decision aid will inform Veterans more fully about the long-term disadvantages of endovascular repair, we hypothesize that the decision aid will reduce the proportion of Veterans who prefer endovascular repair by 25%, based on similar decision aids studied in surgical settings in breast cancer and back pain¹⁶⁻¹⁸.

Table 3 Sample size and power calculations (assuming a 90% baseline rate of EVAR preference)

Number of clusters	Number of patients per cluster	Total Number of Patients	Proportion Choosing Endovascular Repair At	Decision Aid Effect Size (in relative decline in preference)	Proportion Choosing Endovasc Repair at	Power To detect significant difference	Power To detect significant difference	Power To detect significant difference
--------------------	--------------------------------	--------------------------	--	--	--	--	--	--

Intervention	Control	Intervention	Control	Intervention	Control	Control Sites for endovascular	Intervention Sites	(ICC 0.01)	(ICC 0.05)	(ICC 0.10)

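### The Aim 1 model for factors associated with preference names no study-arm term, so associations for survey domains that the decision aid shifts are partly confounded by arm

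*Combined protocol and SAP*

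**What the plan says.** The first Aim 1 hypothesis (Section 1, Specific Aims, H1) concerns predictors of preference. Its durability half reads "Veterans who prioritize concerns about durability will prefer open repair"; the other half links concern about pain or disability to endovascular preference.

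The analysis is in Section 7, Aim 1: "To identify patient characteristics (such as survey responses) associated with preference for endovascular or open repair we will use multivariable mixed effects logistic regression". In the formula given there the covariate term "is a vector of characteristics", and the mixed effects are there to "account for clustering within individual VA centers using a random intercept". Unadjusted and adjusted estimates are both to be reported, the latter "after identifying one or more models to adjust for using for instance stepwise regression or LASSO". No arm term, arm-by-factor interaction, by-arm fit or restriction to controls is stated, and the Aim 1 list of independent variables does not name arm.

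Arm is explicit in the separate comparison of preference between groups, one option for which is "a mixed effects logistic regression with fixed effect of group, and random intercept for center effects".

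The order of events is in Section 4, Step D. At intervention sites, after a short pre-survey, "The Study Coordinator will review the Decision Aid with the Veteran", and only then is the survey given. At control sites the survey comes first, with no aid and no pre-survey listed.

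**The concern.** In the intervention arm the predictor (a survey domain) and the outcome (preference) are both measured after the aid. In the control arm neither is. The Aim 1 power section expects the aid to inform Veterans more fully about the long-term disadvantages of endovascular repair, which is the subject of the durability domain. Arm is thus a plausible common cause of durability concern and open preference.

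If both arms are analysed together without arm, Veterans who saw the aid contribute more durability concern and more open preference, and the model can report an association that exists in neither arm. The reading of H1, and of any other domain that the aid shifts, is at stake. The randomised comparison of preference between arms is not.

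**Working it through.** **Inputs from the documents.** 10 sites per arm, 12 Veterans per site, 120 per arm (Section 4, Recruitment Target). Control EVAR preference 0.90 and a 25% relative decline: 0.90 × 0.75 = 0.675, shown as 0.68 in Table 3. Open preference is then 10% in control and 32% after the aid. ICC 0.01 to 0.10 (Table 3).

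**Assumed, because the documents give no figure.** Share giving priority to durability: 30% in control, 50% or 60% after the aid. No association with preference within either arm (true odds ratio 1.0).

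**The plan's own figure.** None is given for the factor model. For the arm comparison, with effective n = 120/(1 + 11 × ICC) per arm, two-sided alpha 0.05 (assumed) and a t reference on 18 df, power is 0.974 at ICC 0.01 (stated 0.96) and 0.809 at ICC 0.10 (stated 0.81). The inputs are therefore read as the plan intends.

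**Step 1: simple pooling, closed form.** Add the two arms' cell proportions, for 30% and 50%:

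- durability, open: 0.30 × 0.10 + 0.50 × 0.32 = 0.19
- durability, EVAR: 0.30 × 0.90 + 0.50 × 0.68 = 0.61
- no durability, open: 0.70 × 0.10 + 0.50 × 0.32 = 0.23
- no durability, EVAR: 0.70 × 0.90 + 0.50 × 0.68 = 0.97

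Odds ratio = (0.19 × 0.97)/(0.61 × 0.23) = 1.31. For 30% and 60% the cells are 0.222, 0.678, 0.198 and 0.902, and the odds ratio is 1.49. Both ignore site, so they show the mechanism rather than the planned model.

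**Step 2: the center random intercept.** Arm is constant within a center, so within-center information is free of arm and between-center information is not. A random-intercept model uses both, and assumes that the intercept is unrelated to the covariates, which fails here. Simulation of 20 centers × 12 (400 trials per row, one domain in the model) gave, without arm:

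| ICC | Durability, control to aid | Median OR | One-sided rejection (nominal 2.5%) |
|---|---|---|---|
| 0.01 | 30% to 50% | 1.17 | 8.2% |
| 0.01 | 30% to 60% | 1.33 | 12.8% |
| 0.05 | 30% to 50% | 1.11 | 3.2% |
| 0.05 | 30% to 60% | 1.24 | 7.2% |
| 0.10 | 30% to 50% | 1.15 | 5.0% |
| 0.10 | 30% to 60% | 1.14 | 6.5% |

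With arm as a fixed effect the median odds ratio was 0.97-1.04 and rejection 1.2-3.5%.

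**Step 3: independent repeat.** 300 trials per scenario, two-sided 5% tests, outcome coded as EVAR preference (so an odds ratio below 1 points the same way). Without arm, across the three ICCs:

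- prevalence 40%/60%: odds ratio 0.85-0.89, rejection 6-8%
- prevalence 30%/70%: 0.71-0.76, rejection 10-18%
- prevalence 20%/80%: 0.51-0.59, rejection 30-44%

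With arm these became 0.96-1.03 and 2-6%. At equal prevalence (50%/50%) the model without arm gave 0.99-1.03 and 4-7%: no bias when the aid does not move the domain.

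**The case against.** **The omission is by silence.** The formula is offered as an example, the covariate vector is generic, and the neighbouring arm comparison does carry a group effect. A reader might infer that the plan has decided to pool the arms and ignore arm. The text does not say that. Section 4 lists the domains associated with preference among the outcomes on which the intervention is tested, and Aim 2 will study survey variables between the groups, so interest in arm is stated. This stands as to intent. But nothing makes arm a candidate for stepwise or LASSO selection, let alone forces it in, and unadjusted domain estimates would omit it.

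**The bias need not favour H1.** A reader might infer that every domain sensitive to the aid is biased in the hypothesised direction. That is not supported. The aid describes both repair types. If it raised concern about pain together with open preference, pooling would push pain towards open repair, against H1.

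**The size is assumed and can be small.** The shift in durability priority appears nowhere in the documents. The lowest false-positive rate, 3.2% of 400 trials, has a 95% interval of about 1.5-4.9%, which includes 2.5%. The pooled log odds ratio has a standard error of about 0.32, so odds ratios of 1.11-1.33 are a bias of 0.10/0.32 to 0.29/0.32, or about 0.3 to 0.9 standard errors. The simulations used one domain, not the multivariable model with selection. All of this stands.

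**H1 has no decision rule.** No alpha, sidedness or criterion for support is given, so a rate of false support for H1 is not a property of the plan. The rejection rates above only gauge the size of the bias.

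**The pre-survey.** Intervention sites give one before the aid, but no counterpart is listed for control sites, so no common pre-aid measure is described. Its items are in an appendix that was not available.

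**Conclusion.** The concern holds as a specification gap. Fitted as written, the factor model confounds with arm any survey domain that the aid shifts, and the center random intercept removes only part of that. Characteristics that the aid cannot move, such as age, sex and race, are not affected through this route.

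Under the plan's 0.90 and 0.68 and an assumed rise in durability priority from 30% to 50-60%, the odds ratio for a domain with no association within arms is about 1.1-1.3, with a small to moderate excess of false positives. A larger shift gives more bias, and no shift gives none. The size cannot be settled from the documents, nor can the direction for each domain. They do not support a conclusion that H1 will be falsely confirmed.

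**What to change.** In Section 7, Aim 1, state that study arm enters every factor model as a fixed effect, outside any stepwise or LASSO selection, and that this includes the estimates labelled unadjusted for survey domains. Show the H1 domain associations separately by arm as a descriptive supplement. That display would also bear on the Section 4 hypothesis about Veterans who value durability.

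The cost is a sentence or two in the plan and one model parameter. No new data are needed and the arm comparison is unchanged.

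The by-arm estimates will be imprecise, above all in controls, where about 120 × 0.10 = 12 Veterans are expected to prefer open repair. With durability at the assumed 30% and clustering ignored, the control cells are 3.6, 8.4, 32.4 and 75.6, so the standard error of the log odds ratio is √(1/3.6 + 1/8.4 + 1/32.4 + 1/75.6) = 0.66. A 95% interval then spans a factor of about 3.7 either side of the estimate. This is why the by-arm results should be descriptive and the arm-adjusted estimate should carry the conclusion.

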10	10	12	12	120	120	0.9	0.25	0.68	0.96	0.86
10	10	12	12	120	120	0.9	0.20	0.73	0.88	0.75
10	10	12	12	120	120	0.9	0.15	0.78	0.71	0.50

We adjusted our sample size calculations for our cluster-randomized trial to account for intra-cluster correlation, and allow for variable enrollment size within each cluster. As shown in Table 8, we anticipate that we will have 96% likelihood of detecting a 25% effect size, assuming an ICC of 0.01. Sensitivity analyses around our ICC assumption of 0.01 demonstrate that even if our ICC is ten times higher (ICC=0.10), our sample size would still yield an 81% likelihood of detecting a 25% effect size between intervention/control.

Aim 2: To determine the effect of the decision aid on agreement between preferences and repair type.

Aim 2 Dependent and Independent Variables: After identifying Veterans' preference for endovascular or open repair, we will determine the agreement between their preferences and the repair types they receive. The dependent variable will be the kappa statistic (κ), measuring agreement between the preferred repair type and the repair type the Veteran ultimately receives. Cohen's kappa will be compared between the intervention and control groups. Kappa will be calculated overall and by hospital (using a weighted sum of the kappas for each hospital in that arm). As a secondary outcome, Site Study Coordinators will administer two surveys to the Veteran. These two surveys will examine patient satisfaction (PDQ-18) and shared decision making (Decision Process Score, or DPS)^{87, 104}. Our group has used these or similar instruments in prior work^{104, 105}. A survey administration training guide for each Site Study Coordinator has been developed. The DPS will be administered at the end of the visit, and the PDQ-18 will be completed at 30-day follow-up visits which are already standard practice after AAA repair for both repair types. Completing the surveys in this context will not require any extra visits by Veterans, an important strength given the elderly population of patients involved in our proposal.

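### Table 3 (Aim 1 power): two intervention proportions do not match their stated declines, and the text's 81% cannot be reconciled with the table's 0.86

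*Combined protocol and SAP*

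**What the plan says.** The Aim 1 power analysis in Section 7 rests on Table 3, which is headed as "assuming a 90% baseline rate of EVAR preference". The effect column is labelled "Decision Aid Effect Size (in relative decline in preference", so each intervention proportion should be 0.9 × (1 − decline). Every row has 10 sites per arm and 12 patients per site.

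The three rows read:

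- 25% decline: "10 10 12 12 120 120 0.9 0.25 0.68 0.96 0.86"
- 20% decline: "10 10 12 12 120 120 0.9 0.20 0.73 0.88 0.75"
- 15% decline: "10 10 12 12 120 120 0.9 0.15 0.78 0.71 0.50"

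The power columns are headed "ICC 0.01) (ICC 0.05) (ICC 0.10". Only two powers per row can be read in the available text. The third may have been lost when the PDF was converted, and I do not count it as an error.

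Below the table, the text says "we will have 96% likelihood of detecting a 25% effect size, assuming an ICC of 0.01", and that at ICC 0.10 "our sample size would still yield an 81% likelihood of detecting a 25% effect size". It cites Table 8 for these results, although the figures belong to Table 3. It also says that variable enrolment across sites was allowed for, but gives no CV of site size. No alpha, sidedness or formula is given for Aim 1.

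**The concern.** Two intervention proportions look wrong by simple multiplication. The powers also do not seem to follow from the inputs printed beside them. The fall from 0.86 to 0.81 in the 25% scenario looks too small for a doubling of the ICC.

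Readers use these figures to judge what 240 patients at 20 sites can detect. The 81% matters most, because it is the plan's evidence that power survives an ICC ten times the assumed value. Without a CV, alpha or formula, a reader cannot repair the table.

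**Working it through.** **Inputs.** From Table 3: control proportion 0.90; declines 0.25, 0.20, 0.15; 10 sites per arm; m = 12 per site; ICC 0.01, 0.05, 0.10. My assumptions, as Aim 1 states neither: two-sided alpha 0.05, and CV from 0 (equal sites) to 0.7. I read the two visible powers per row as ICC 0.01 and 0.05, because the text ties 0.96 to ICC 0.01.

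**Step 1: proportions.**

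- 25%: 0.9 × 0.75 = 0.675, printed 0.68 (correct to rounding).
- 20%: 0.9 × 0.80 = 0.72, printed 0.73. Implied decline 1 − 0.73/0.9 = 18.9%.
- 15%: 0.9 × 0.85 = 0.765, printed 0.78. Implied decline 1 − 0.78/0.9 = 13.3%.

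The printed series 0.68, 0.73, 0.78 rises by 0.05 per row, which may be how the slip arose.

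**Step 2: powers at the printed inputs.** Design effect = 1 + [(1 + CV²)m − 1] × ICC. With CV = 0 this is 1.11, 1.55 and 2.10. Noncentrality = (p1 − p2) / √{[p1(1 − p1) + p2(1 − p2)] × design effect / 120}, referred to a noncentral t with 18 df.

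- At 0.68, ICC 0.05: 0.22 / √(0.3076 × 1.55/120) = 3.49, power 0.91 (printed 0.86).
- At 0.78, ICC 0.01: 0.12 / √(0.2616 × 1.11/120) = 2.44, power 0.64 (printed 0.71).

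| Printed proportion | ICC 0.01: computed (printed) | ICC 0.05: computed (printed) |
|---|---|---|
| 0.68 | 0.974 (0.96) | 0.910 (0.86) |
| 0.73 | 0.877 (0.88) | 0.752 (0.75) |
| 0.78 | 0.636 (0.71) | 0.498 (0.50) |

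The same formula gives 0.809 for 0.68 at ICC 0.10, matching the text's 81%. So it comes within 2 points of five of the seven stated figures and misses 0.86 and 0.71. A pooled z test misses all six cells by more than 2 points (0.982/0.927, 0.902/0.783, 0.675/0.531). With m held at 12 and two-sided alpha, I tried eight power formulas, both sets of proportions and 51 CV values from 0 to 1.0 (8 × 2 × 51 = 816 settings). None put all six cells within 2 points.

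**Step 3: 0.86 against 81%.** For a fixed effect and sample size, (1.96 + z for power)² × design effect must be constant across ICCs.

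- Power 0.86: (1.960 + 1.080)² = 9.24. Power 0.81: (1.960 + 0.878)² = 8.05.
- Design-effect ratio implied by the two powers: 9.24/8.05 = 1.15. With both powers at the edge of rounding (0.865 and 0.805), it is at most 1.18. The t test with 18 df gives the same ratios.
- Ratio required from ICC 0.05 to 0.10 with 12 per site: 2.10/1.55 = 1.35 for equal sites. At CV 0.7 it is 2.688/1.844 = 1.46, so unequal sites widen the gap.

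If 0.86 is instead the ICC 0.10 power, it contradicts 81% directly.

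**Step 4: powers at the exact declines** (t, 18 df, m = 12, equal sites), ICC 0.01/0.05/0.10:

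- 25%: 0.978/0.920/0.824
- 20%: 0.906/0.792/0.664
- 15%: 0.724/0.581/0.460

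At CV 0.6 the design effects are 1.153, 1.766 and 2.532, and the 25% row becomes 0.974/0.883/0.750.

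**The case against.** The plan says that it allowed for variable site sizes, so an equal-site benchmark leaves out an adjustment it claims to have made. This objection stands in part. Against the exact declines with equal sites, every stated power is slightly low, which is the direction that unequal sites produce.

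A reader might infer that the table's powers cannot come from any single calculation. That is too strong for the six visible cells. With exact declines, 11.6 per site and CV 0.6, the t test with 18 df gives 0.970/0.878, 0.886/0.731 and 0.696/0.520, all within 2 points of print. Such fits are rare: when m, CV and sidedness were all allowed to vary, 3 of 7,392 settings succeeded, each with a worst cell 1.96 to 1.98 points off. All need fewer than the stated 12 per site and a CV that the plan does not give. They yield about 0.74 to 0.75 at ICC 0.10, not 0.81.

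A reader might also infer that 0.71 overstates power. That holds only at the misprinted 0.78. At the exact 15% decline with equal sites the value is 0.72, so charging 0.71 as too high would count one slip twice.

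Finally, the column placement of 0.86 is inferred. The conflict with 81% does not depend on it, since both possible placements fail.

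**Conclusion.** The point holds in three parts. The proportions 0.73 and 0.78 are wrong by 1 and 1.5 percentage points, whatever power method was used. The powers are not reproducible from the inputs that the table prints, with gaps of 5 points (0.86 against 0.91) and 7 points (0.71 against 0.64) under the t calculation. The text's 81% cannot be reconciled with the table's 0.86.

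The documents do not show that the trial is underpowered for its hypothesised 25% effect. With exact declines and equal sites, power at ICC 0.10 is about 0.82, close to the stated 81%. It falls to about 0.75 if the CV is 0.6, so the reassurance in the text depends on a number that the plan omits. These values assume two-sided alpha 0.05 and a t test with 18 df. This is a correction to stated figures, not a challenge to the design.

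**What to change.** Set the intervention proportions to 0.675, 0.72 and 0.765. Recompute all nine powers with one stated method, giving alpha, sidedness and the assumed CV of site size. The method should be consistent with the planned comparison (Mantel-Haenszel or mixed-effects logistic regression). The t calculation used here is only a check and need not be adopted. Replace the 96% and 81% in the text with the recomputed values, and point the text to Table 3 rather than Table 8. The cost is one recalculation, a replaced table and two edited sentences, with no change to design or conduct.
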